8.5. Trial Regimen

There will be an initial dose escalation in adults and children to confirm safety of a lower dose of AdCh63 ME-TRAP before using the full dose.

Group 1:

[figure not shown]
Volunteers in group 1B will not be vaccinated until a minimum of 14 days have elapsed following vaccination of volunteers in group 1A, following safety review by the LSM and DSMB.

To avoid a previously unsuspected AE affecting multiple volunteers, one volunteer in group 1A will be vaccinated alone. 48 hours later a further two volunteers will be vaccinated. This is to allow safety assessment by Investigators. In the absence of significant safety concerns affecting these initial volunteers at 48 hours post-vaccination, the remaining volunteers in this group will be vaccinated.

Groups 2 and 3:

Vaccination of volunteers in groups 2 & 3 will not begin until a minimum of 14 days have elapsed following vaccination of volunteers in group 1B, and a safety review of adverse event data for groups 1A & 1B has been reviewed by the LSM & DSMB.

The following flow chart outlines the regimen for vaccination of volunteers in groups 2 and 3.

In stage 1a, two volunteers from group 2A and one control volunteer from group 2C will be immunised simultaneously, with AdCh63 ME-TRAP 1 x 10¹⁰ vp and HDCRV, respectively. The remaining volunteers in groups 2A and 2C will be vaccinated after 48 hours have elapsed, providing there are no safety concerns affecting these initial volunteers.

Stage 2a will not proceed until approval is granted following 14 day safety monitoring following stage 1a. One volunteer from group 2B and two volunteers from group 3A will be immunised simultaneously, with AdCh63 ME-TRAP 1 x 10¹⁰ vp and AdCh63 ME-TRAP 5 x 10¹⁰ vp, respectively. The remaining volunteers in groups 2B and 3A will be vaccinated after 48 hours have elapsed, providing there are no safety concerns affecting these initial volunteers.

Stage 3a will not proceed until approval is granted following 14 day safety monitoring following stage 2a. All volunteers in groups 3B and 3C may be vaccinated simultaneously.

In stage 1b, two volunteers from group 2A and one control volunteer from group 2C will be immunised simultaneously, with MVA ME-TRAP 1 x 10^8 pfu and HDCRV, respectively. The remaining volunteers in groups 2A and 2C will be vaccinated after 48 hours have elapsed, providing there are no safety concerns affecting these initial volunteers.

[figure not shown]
Stage 2b will not proceed until approval is granted following 14 day safety monitoring following stage 1b. One volunteer from group 2B and two volunteers from group 3A will be immunised simultaneously, with MVA ME-TRAP 2 x 10^8 pfu and MVA ME-TRAP 1 x 10^8 pfu, respectively. The remaining volunteers in groups 2B and 3A will be vaccinated after 48 hours have elapsed, providing there are no safety concerns affecting these initial volunteers.

Stage 3b will not proceed until approval is granted following 14 day safety monitoring following stage 2b. All volunteers in groups 3B and 3C may be vaccinated simultaneously.

Results of the FBC, creatinine and ALT will be reviewed before any immunisation is administered. Results of blood tests will be communicated to volunteers/their carers on their next clinic visit.

8.6. Labeling and Packaging

Example vial labels (these are included for example only and are subject to change):

8.7. Accountability

All movements of vaccines will be documented in vaccine accountability logs according to local site SOPs.

8.8. Revaccination exclusion criteria

Anaphylactic reaction following administration of vaccine constitutes an absolute contraindication to further administration of vaccine. If this occurs during the study, the subject will be withdrawn and followed until resolution of the event, as with any serious adverse event.

9. STUDY SCHEDULE

9.1. Screening

The MRC study team will hold local community meetings and explain the study to potential participants and the carers of potentially eligible children. During these meetings the investigators will explain the following: the need for a vaccine (including a simple picture of the burden of malaria on the community); the current status of vaccine development (including the fact that this is likely to be a prolonged process); the study screening and informed consent procedure; risks of vaccination and the unproven benefits of vaccination. It will be stressed that this is an experimental vaccine and cannot be guaranteed to provide protection, and that it will therefore still be necessary to seek treatment for possible malaria even after vaccination. It will be stressed that some of the children enrolled in the study will receive a rabies vaccine and not the malaria vaccine, but that at the end of the trial all volunteers in groups 2 and 3 will be offered the standard rabies immunization (not as part of the trial protocol). It will be made clear that carers will not know which vaccine their child has received until the end of the study. Potential participants and their carers will be informed that we will request HIV testing for volunteers. We will explain that we would plan eventually to offer immunisation to those testing HIV positive, but that normal practice is to begin with those who are HIV negative. In order to preserve the confidentiality of those volunteers infected with HIV who are undergoing immunisation, we will not discuss the option of immunisation for those testing positive publicly, since it may lead to speculation regarding the identity of those infected with HIV, particularly if there are a variety of different regimens being used. It will also be made clear to the carer of prospective volunteers that a photograph of the child and carer will be taken to aid identification of the study participant.

After this meeting the field worker(s) will identify potential volunteers and invite them to the Sukuta Health Centre for further discussion. During these discussions, it will be stressed that this is the beginning of a long process of vaccine development, which will be accelerated by the conduct of such small trials in Africa.

At Sukuta Health Centre field workers will explain the study further to each volunteer/their carer on an individual basis. Individuals who feel that the trial is appropriate for them or their child will be invited to attend a formal screening visit. This will include a further discussion of the study with the principal investigator or study physician, and another opportunity for private discussion.

Screening visit

We will provide detailed information about the study for distribution to the volunteers/carers. The principal investigator will endeavour to ensure that all volunteers/carers fully understand the risks. Any volunteer/carer who appears to have less than complete understanding will not be enrolled. As with any experimental vaccine the volunteers/carers must understand that the vaccines have not yet been shown to prevent infection and this will be stressed during the recruitment stage. They must also understand the very small chance of anaphylactic reactions and thereby the importance of complying with the one-hour observation period after each vaccination. The information sheet covers these points in detail, and each volunteer will have the contents of the sheet explained in individual meetings on 2 separate occasions, including a quiz/ comprehension test administered prior to signing/thumb printing the form. This process is similar to that used previously and we believe has produced a high standard of informed consent.

At the screening visit following written informed consent investigators will take a clinical history, examine all volunteers carefully and conduct a number of standard laboratory tests (FBC, malaria rapid antigen test, ALT and creatinine, and dipstick urinalysisfor protein and blood to screen subjects for clinically significant acute or chronic diseases. Those with abnormal results at screening will be offered appropriate investigations and treatment or referral as necessary. Malaria antigen test positive children will be excluded from the study. An identification photograph will also be taken, as above. This will be identified by the unique study number and will be destroyed at the end of the study.

When the results of these screening investigations are available a vaccination visit will be arranged, not more than 90 days following the screening visit.

HIV testing

Volunteers/carers will have access to a trained counsellor. Volunteers will have the option to enrol without being informed of their status, although our experience previously was that all volunteers wished to know their status.

HIV serostatus (positive and negative) will be established using the standard diagnostic methods in place at the MRC Fajara. Results will be disclosed after the initial test, with an explanation that confirmatory testing is needed for those who are HIV seropositive.

We would offer follow up counselling to support further those diagnosed HIV positive. Those diagnosed positive would receive standard medical care at a local Government facility, according to Gambia Government guidelines.

9.2. Enrolment

Volunteers are considered enrolled into the study when they receive their first vaccination. This will occur not more than 90 days following the screening visit.

9.3. Follow-up

Volunteers are followed until 300 days (approximately 10 months) after the first vaccination.

Field workers will assess and record local adverse reactions including pain, swelling, discolouration and limitation of arm movement. He or she will then assess and record systemic adverse events as outlined in section 11.2. Each solicited side effect will be classified as absent, mild, moderate or severe. Due to the high anticipated background frequency of illness in children in this area, solicited and unsolicited adverse events will only be recorded up to 30 days after each vaccination for volunteers in group 2 and 3. Serious adverse events will be collected throughout the study period. Each volunteer will be visited at home daily for three days by a field worker after each vaccination and if necessary the volunteer will continue to be seen regularly until the symptom(s) have resolved. In addition the volunteers will be seen on day 14, day 63, day 90 and day 300 after vaccination for full safety and reactogenicity assessment by the Principal Investigator. Volunteers will be asked to present to the clinic if they develop any illness up to 56 days after vaccination. The emerging safety data will be described to the volunteers when they attend for the next immunisation.

Rabies immunisation will be arranged by the PI for all participants in groups 2 and 3, although this will not be covered by the trial protocol.

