Group 3 (Aged 2-6)	В	6 volunteers	AdCh63 ME-TRAP 5 x 10 ¹⁰ vp	MVA ME-TRAP 2 x 10 ⁸ pfu		
(,,,,,,,,,,,,,,,,,,,,,,,,,,,,,,,,,,,,,,	С	6 volunteers	HDCRV 1ml	HDCRV 1ml		

	Clinic Attendance	1	2	3	4	5	6	7
	number							
	Timeline (days)*	S	D0	D14	D56	D63	D90	D300
	Time windows (days)			±7	-7/+30	-1/+7	±14	±28
	Vaccination		1		2			
	Inclusion/Exclusion	Х						
	criteria							
	Informed consent	Х						
	Medical history	Х						
	Phys. exam.	Х						
	Urinalysis	Х						
	Review contra-	Х	Х		Х			
	indications							
	Post-dose follow-up			14	56	7	34	244
	(days)**							
	Local & systemic		Х	Х	Х	Х	Х	Х
	events/reactions							
	HLA typing (mL)	3						
	P. falciparum PCR		2					
	HIV (mL)	3						
GROUP 1	GROUP 1: Exploratory	7	27	30	30	30	30	30
	immunology (incl							
	ELISPOT) and safety							
	bloods (mL)							
	GROUP 1: Blood	10	30	30	30	30	30	30
	volume (mL)							
	GROUP 1: Cumulative	10	40	70	100	130	160	190

	blood volume (mL)							
GROUPS	GROUPS 2 & 3:	5***	5****	5	5	5	5	5
2&3	Blood volume (mL)							
	GROUPS 2 & 3:	5	10	15	20	25	30	35
	Cumulative blood							
	volume (mL)							

*Timeline is approximate only. Exact timings of visits relate to the previous visit – *i.e.* each visit must occur the specified number of days after the last visit \pm time window

** Volunteers will be followed up daily at home by a field worker for a minimum of three days following each vaccination

*** Includes HLA

**** Includes *P. Falciparum* PCR

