10. STUDY PROCEDURES

10.1. Clinical Evaluations

Screening Visit:

Medical history and physical examination will be performed at screening to exclude any significant medical conditions as described in Section 5.2. HLA typing will also be performed on blood taken at this visit, as outlined in Section 10.3.

D0 (Vaccination with AdCh63 ME-TRAP)

Medical history, temperature monitoring +/- physical examination will be performed and eligibility will be reviewed by the Investigator prior to vaccination. Vaccine will be administered as outlined in Section 8.4. Venepuncture for exploratory immunology and *Plasmodium falciparum* polymerase chain reaction will be performed as outlined in Section 10.3. As outlined in Sections 4.3.2 and 10.3.2, *P. falciparum* PCR testing will be performed at a later stage, the results will be used in the interpretation of immunogenicity data, and this assay is not validated for clinical diagnostic purposes. As such, PCR results will have no impact on the conduct of the study.

D1, 2 and 3

Each volunteer will be visited at home daily for three days by a field worker for assessment and recording of any solicited and unsolicited AEs in the CRF. If necessary the volunteer will continue to be seen regularly until the symptom(s) have resolved or stabilised.

D14 (+/-7 days)

Medical history, temperature monitoring +/- physical examination will be performed and recorded in the CRF. Any solicited and unsolicited AEs will be recorded. Venepuncture will be performed for FBC, ALT, Creatinine and exploratory immunology as outlined in Section 10.3.

D56 (Vaccination with MVA ME-TRAP) (- 7/ +30 days)

Medical history, temperature monitoring +/- physical examination will be performed and eligibility will be reviewed by the Investigator prior to vaccination. Vaccine will be administered as outlined in Section 8.4. Venepuncture will be performed for FBC, ALT, Creatinine and exploratory immunology as outlined in Section 10.3.

D57, 58 and 59

Each volunteer will be visited at home daily for three days by a field worker for assessment and recording of any solicited and unsolicited AEs in the CRF. If necessary the volunteer will continue to be seen regularly until the symptom(s) have resolved or stabilised.

D63 (-1/+7 days)

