At each visit subjects will be requested to report local and general side effects they might have experienced since they last were seen. These will only be recorded in the CRF if they occurred up to 30 days post vaccination, unless they meet the criteria for serious adverse event as outlined below. The investigator will assess the severity of the solicited signs and symptoms using the key provided in Tables 4 and 5.

GRADE 0	None	
GRADE 1	Mild: Transient or mild discomfort (< 48 hours); no medical intervention/therapy	
	required	
GRADE 2	Moderate: Mild to moderate limitation in activity - some assistance may be needed; no	
	or minimal medical intervention/therapy required	
GRADE 3	Severe: Marked limitation in activity, some assistance usually required; medical	
	intervention/therapy required.	

Table 4: Intensity of the general adverse events in adults will be assessed	as described.
Table 4: Intensity of the general adverse events in adults will be assessed	as described:

Table 5: Intensity of the general adverse events in children (aged 2-6) will be assessed as described:

Systemic (General)	Grade 1	Grade 2	Grade 3
Fever (axillary temp)	≥38C- ≤39C	≥39C - ≤40C	≥40C
Decreased oral intake	Minimal decrease in oral	Below 50% of normal	No oral intake in
	intake	oral intake in 24 hr	24hr
Vomiting	1 episode in 24hr; no	2-3 episodes in 24 hr	> 3 episodes in 24
	interference with activity	OR some interference	hours OR prevents
		with activity	daily activity
Diarrhea	Unformed stool OR 1-3	Partially liquid stools	Completely liquid
	more stools than	OR 4-6 more stools	stools OR >6 more
	baseline in 24 hr	than baseline in 24hr	stools than baseline
			in 24 hr
Reduced activity	Minimal interference	Below 50% of normal	Prevents daily
	with activity	activity in 24 hr	activity
Unsolicited adverse	Minimal interference	Below 50% of normal	Prevents daily
events	with activity	activity in 24 hr	activity

Activity for the purposes of this assessment will be considered oral intake, sleep and play.

The investigator using the guidelines provided in section 11.3.8. will assess the relationship of the event to the administration of the vaccine. Both severity of the event and its relationship to the vaccine administration will be documented in the CRF if occurring up to 30 days post vaccination for groups 2 and 3, unless it fulfils criteria for a serious adverse event (section 11.3.5).

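### For children, the ±14-day window lets the D90 visit fall before day 30 after the boost, leaving up to 11 of the 30 recorded days unasked about until D300

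*Protocol*

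**What the plan says.** Four elements of the protocol matter here.

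- **Recording period.** Section 9.3 states that "solicited and unsolicited adverse events will only be recorded up to 30 days after each vaccination for volunteers in group 2 and 3". This limit does not apply to serious adverse events, which are collected throughout the study.
- **Scheduled contacts.** Section 9.3 provides that "Each volunteer will be visited at home daily for three days by a field worker after each vaccination", with further visits if symptoms persist. The clinic visits in section 10.1 are D14 (±7), D56 for the boost (−7/+30), D63 (−1/+7), D90 (±14) and D300 (±28). The grid in section 1 marks local and systemic events at D0 and at all five of these visits.
- **Anchoring of windows.** The footnote to the grid says that "each visit must occur the specified number of days after the last visit", give or take the window. Windows are therefore chained from visit to visit and do not run from the dose.
- **Elicitation between visits.** Section 11.3.6: "At each visit subjects will be requested to report local and general side effects they might have experienced since they last were seen". It adds: "These will only be recorded in the CRF if they occurred up to 30 days post vaccination", with serious events exempt. Section 9.3 also provides that "Volunteers will be asked to present to the clinic if they develop any illness up to 56 days after vaccination".

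Section 4.3.1 makes solicited and unsolicited vaccine-linked adverse events the primary endpoint.

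**The concern.** A fixed 30-day recording period works best when a scheduled contact falls on or shortly after its last day. The carer is then asked once about all of it while memory is fresh. After the boost, D90 does this job at its nominal date, but its window is wide enough to put the visit well inside the 30 days. When that happens, no scheduled visit asks about the end of the period for months. The carer must then also place the onset before or after day 30 from memory, because that decides whether the event is recorded at all.

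At stake is the completeness of mild and moderate events in children, which form part of the primary endpoint. Sections 2.2 and 4.1 justify the paediatric control arm by the expected high rate of concurrent illness, so the background count in controls needs complete capture as well.

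**Working it through.** **Inputs.** Visit days 0, 14, 56, 63, 90 and 300, their windows and the chaining rule come from section 1; the windows are repeated in section 10.1. The 30-day period comes from section 9.3.

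**The plan's own figures.** The post-dose follow-up row of the grid gives 14, 56, 7, 34 and 244 days. These are 14−0, 56−0, 63−56, 90−56 and 300−56, so they reproduce.

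**Boost, nominal timing.** D63 is boost+7 and D90 is boost+34. Days 8 to 30 are asked about at D90, with recall of 34−30 = 4 to 34−8 = 26 days. The period is fully covered.

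**Boost, earliest compliant D90.**

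| | Windows chained to the previous visit | Window anchored to the dose |
|---|---|---|
| Earliest D63 | 7−1 = boost+6 | – |
| Earliest D90 | 6+(27−14) = boost+19 | 34−14 = boost+20 |
| Recorded days after that visit | 30−19 = 11 (days 20–30) | 30−20 = 10 (days 21–30) |
| Share of the 30 days | 11/30 = 37% | 10/30 = 33% |
| Interval from that D90 to D300 | 210±28 = 182–238 days | (244−28)−20 = 196 to (244+28)−20 = 252 days |

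These intervals are about 6 to 8 months.

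**How much of the window is affected.**

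- Anchored: D90 may fall on boost+20 to boost+48, which is 29 days. Of these, 10 (days 20 to 29) lie before day 30.
- Chained: D63 has 9 permitted days (6 to 14) and the D63-to-D90 gap has 29 (13 to 41), giving 9×29 = 261 combinations. Those with D90 before day 30 number 11+10+9+8+7+6+5+4+3 = 63, or 24%.

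These are counts of permitted dates, not predicted frequencies. The protocol does not say how visits will spread over the window.

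**Prime, for comparison.** If D14 falls on day 7, 14 or 21, then 23, 16 or 9 recorded days follow it. The next scheduled contact is D56, whose look-back covers all of them. With D14 and D56 at nominal timing, recall for days 15 to 30 is 56−30 = 26 to 56−15 = 41 days. With D56 at day 86, the end of its nominal window, it is 56 to 71 days. The D56 entry in section 10.1 does not itself mention adverse events, but the grid marks them there and the section 11.3.6 question applies at each visit.

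**The case against.** The best defence is that the follow-up is deliberately front-loaded. Section 4.1 places the crucial safety assessment in the first 72 hours, when most vaccine-related events are reported, and daily home visits by blinded field workers cover that time. D14 and D63 fall inside the 30-day periods. Every visit asks back to the previous one, D300 included, and carers are asked to bring the child with any illness up to day 56. Escalation between stages uses 14-day safety profiles (section 4.4.1), so days 20 to 30 after the boost do not enter those decisions. The 11-day figure also needs both D63 and D90 at their earliest dates. All of this stands, and it limits the point to the tail of the period. It does not explain why the window should admit a D90 visit before the recording period ends.

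A reader might infer more than the document supports:

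- **That the recording period is not actively observed.** It is, through the contacts just listed. The since-last-seen question also means that every recorded day is eventually asked about.
- **That D90 is the last contact.** D300 also records adverse events. The weakness is the length of recall, not the absence of a later question.
- **That the comparisons are biased.** The visit schedule is the same for vaccine and control children, so the intended recall is the same in every arm. Equal under-reporting can shrink absolute differences but need not change ratios. Section 12.1 names comparisons of two AdCh63 doses and of two MVA doses in children. AdCh63 events against MVA events is not among them, so unequal recall after prime and boost disturbs no planned comparison.
- **That the sections contradict each other.** They do not. The window and the recording period are simply poorly matched.

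**Conclusion.** The point holds in this limited form. Under the protocol's chaining rule a compliant D90 visit can fall on boost+19, leaving 11 of the 30 recorded days to self-presentation and to recall at D300, 182 to 238 days after D90. If the window runs from the dose instead, the figures are boost+20, 10 days and 196 to 252 days. At nominal timing nothing is left uncovered.

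The size in practice depends on two things that the protocol does not give: how often D90 is held early, and how many mild events carers neither present with nor remember. The expected effect is some loss of mild and moderate non-serious events late in the period after the boost, in all paediatric arms. Serious adverse events fall outside the 30-day limit and are collected throughout. The matter is worth correcting because it touches the primary endpoint and the correction is cheap.

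The tail after the prime is a limitation to acknowledge: nominally days 15 to 30, or 9 to 23 days depending on D14, covered only by the D56 look-back.

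**What to change.** For groups 2 and 3, define the D90 window relative to the boost, with a lower limit no earlier than 30 days after it. An example is −4/+14 days around boost+34, that is, boost+30 to boost+48. Anchoring to the boost is needed: under chaining, a −4 limit would still allow 6+(27−4) = boost+29. State this as an exception to the chaining footnote in section 1, and make the same change in section 10.1.

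The cost is slightly less scheduling freedom. In the example 19 dates remain of the 29 allowed when the window is anchored to the dose; the upper limit can be set separately. No visit, blood sample or staff time is added.

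Also note in the protocol that days after D14 in the period following the prime rest on recall at D56 and on self-presentation. An extra home contact at day 30 after the prime would shorten that recall, but it means 36 more visits. That is a trade-off for the sponsor and not a necessary correction.

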Further details for any AE (such as start/stop date and any treatment) will also be gathered, regardless of the relationship to the vaccine in sufficient detail to also allow assessment of the AE according to case definitions published by the Brighton Collaboration [62]. Space is allocated on the CRF to document any unsolicited adverse event reported by the volunteer/carer up to day 30 post-vaccination for groups 2 & 3, and throughout the study period for group 1. Serious adverse events (SAE) as defined in section 11.3.5 of the protocol will be documented in the CRF and reported as described.

Adverse events will not be collected on volunteers in groups 2 and 3 given rabies vaccine at the end of the trial.

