11.3.8. Reporting of Adverse Events

Every SAE occurring throughout the trial must be reported by telephone, email or fax to the sponsor, LSM and DSMB by the investigator as soon as (s)he is alerted of it and within one working day, even if the investigator considers that the adverse event is not related to vaccination. The investigator will then complete a SAE report form as soon as possible and within five working days or seven calendar days.

Any relevant information concerning the adverse event that becomes available after the SAE report form has been sent (outcome, precise description of medical history, results of the investigation, copy of hospitalisation report, etc.) will be forwarded to the Sponsor in a timely manner. The anonymity of the subjects shall be respected when forwarding this information.

SAEs that are suspected to be related to the vaccine will be reported to the Ethics Committee within 15 calendar days of the site becoming aware of the event. If the event is fatal or life-threatening, the event will be reported within 7 calendar days.

Suspected unexpected serious adverse reactions (SUSARs) will be reported according to national regulatory guidelines. The sponsor pledges to inform the Authorities of any trial discontinuation and specify the reason for discontinuation.

The causal relationship between the AE and the product will first be evaluated by the investigator with the following scale:

No relationship: No temporal relationship to study product; and Alternate aetiology (clinical state, environmental or other interventions); and Does not follow known pattern of response to study product

Possible relationship: Reasonable temporal relationship to study product; or Event not readily produced by clinical state, environmental or other interventions; or Similar pattern of response to that seen with other vaccines

Probable relationship: Reasonable temporal relationship to study product; and Event not readily produced by clinical state, environment, or other interventions or Known pattern of response seen with other vaccines

Definite relationship: Reasonable temporal relationship to study product; and Event not readily produced by clinical state, environment, or other interventions; and Known pattern of response seen with other vaccines

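### The request that volunteers report illness lapses about 188 days before serious-event collection ends, and no contact is planned in that interval before the D300 visit

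*Protocol*

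**What the plan says.** All of this is in the protocol.

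- **Length of follow-up (9.3):** "Volunteers are followed until 300 days (approximately 10 months) after the first vaccination".
- **Request to volunteers (9.3):** "Volunteers will be asked to present to the clinic if they develop any illness up to 56 days after vaccination". It does not say whether the 56 days run from each dose or only from the first.
- **Serious events (9.3):** "Serious adverse events will be collected throughout the study period". This covers every group.
- **Non-serious events, children (9.3):** "solicited and unsolicited adverse events will only be recorded up to 30 days after each vaccination for volunteers in group 2 and 3".
- **Non-serious events, adults (11.3.6):** one sentence provides CRF space for unsolicited events "up to day 30 post-vaccination for groups 2 & 3, and throughout the study period for group 1". An earlier sentence in the same section, on events reported at visits, says "These will only be recorded in the CRF if they occurred up to 30 days post vaccination". It exempts serious events but names no group.
- **Contacts (1, 9.3, 10.1):** vaccination at D0 and D56, three daily home visits after each dose, and clinic visits at D14, D63, D90 and D300. Nothing is scheduled between D90 and D300. At each visit volunteers are asked about events since they were last seen (11.3.6).
- **SAE reporting (11.3.8):** the investigator reports to the sponsor, local safety monitor and DSMB "as soon as (s)he is alerted of it and within one working day".

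**The concern.** Safety is the primary objective, and SAE collection has no cut-off before the end of the study. The one sentence that asks volunteers to come forward between visits does have a cut-off, and it falls well before D300. After it lapses, the next planned contact is the final visit.

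The cost is mainly timeliness, with some risk to completeness. The SAE clock in 11.3.8 starts when the investigator is alerted. Under the plan as written, nothing scheduled produces that alert for several months. A vaccine-related admission late in follow-up is among the things the discontinuation criteria in 4.4.2 are meant to act on, and it could first surface at D300. Families also recall events less reliably after many months than when asked at the time. A report of no late SAEs would then be weaker evidence than it appears.

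**Working it through.** The protocol gives no figure for this interval, so there is nothing of its own to reproduce. As a check on the schedule, the intervals from the D56 vaccination are 63 − 56 = 7, 90 − 56 = 34 and 300 − 56 = 244 days. These match the post-dose follow-up row of the table in section 1.

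**Inputs.** Doses at D0 and D56; request window 56 days (9.3); visits at D63 (−1/+7), D90 (±14) and D300 (±28); the section 1 footnote that times each visit from the previous one; 36 children and 16 adults (12.2).

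**Reading A: the window follows each dose.**
- Request ends at 56 + 56 = D112.
- Remaining days: 300 − 112 = 188, and 188/300 = 62.7%.
- The D90 visit falls before the request lapses, so the D300 visit is the only scheduled contact in the gap.

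Visit windows under reading A, counted from the boost:

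| Step | Shortest | Nominal | Longest |
|---|---|---|---|
| Boost to D63 visit | 6 | 7 | 14 |
| D63 to D90 visit (27 ± 14) | 13 | 27 | 41 |
| D90 to D300 visit (210 ± 28) | 182 | 210 | 238 |
| Boost to final visit | 201 | 244 | 293 |
| Less the 56-day window | **145** | **188** | **237** |

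The D90 visit is 6 + 13 = 19 to 14 + 41 = 55 days after the boost, so it always precedes the lapse at 56 days.

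**Reading B: the window follows the first dose only.**
- Days outside the window: 300 − 56 = 244 (81.3%).
- The D63 and D90 visits fall within those days. The part that depends on the final visit alone is 300 − 90 = 210 days (70%).

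**Consequence on the nominal schedule, reading A.**
- An admission on D113 might first be elicited at D300, which is 300 − 113 = 187 days later.
- SAE person-time without a request or planned contact before the final visit, assuming full retention: children 36 × 188/365.25 = 18.5 years; adults 16 × 188/365.25 = 8.2 years.

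**Which events are affected.**
- SAEs, all groups: collection runs to D300, so the gap applies.
- Non-serious events, children: recording stops 30 days after each dose. Under reading A that lies inside the request window, so there is no gap. Under reading B the 30 days after the boost fall outside the request, but the post-boost home visits and the D63 visit fall within those days, and the D90 visit follows nominally at 34 days.
- Non-serious events, adults: undetermined. The CRF-space sentence in 11.3.6 runs to the end of the study, while the other 11.3.6 sentence stops at 30 days without naming a group. The D300 entry in 10.1, which records any adverse events, fits the first. Section 11.3.7, which assesses outcome for non-serious events within 30 days, fits the second.

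**The case against.** The strongest reply is that a time-limited request covering any illness, minor illness included, does not contradict longer collection of serious events. Section 9.3 never tells volunteers that reporting ends at 56 days. Events are still sought at D300 through the medical history and the question about events since the last visit. Other routes also exist:

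- free health care during the study (16.4);
- history and examination directed at specific events at other times, at the investigators' discretion (10.1);
- the advice in 9.1 to keep seeking treatment for possible malaria;
- SAE reporting whenever the investigator learns of an event (11.3.8).

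The information sheet mentioned in 9.1 is not available for review and may ask for more. Section 4.1 also places the crucial safety assessment in the first 72 hours.

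Much of this stands and limits the point. A reader might infer that late safety data rest wholly on recall at one visit, or that nobody was asked about late events. The documents do not support either, given the routes above and the D300 questioning. A reader might also infer that the one-working-day rule or the discontinuation criteria could not operate. That goes too far. The reporting clock starts only on alert, so late awareness does not breach it. Section 4.4.2 can also be triggered by SAEs in other ongoing studies of the products, by new published information, or at the Principal Investigator's discretion.

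What the reply does not do is supply a planned prompt. Free care appears under inducement and is not linked to SAE capture. Event-directed assessment presupposes that the event is known. The reporting rule governs what follows the alert, not how the alert arises.

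**Conclusion.** The point holds for SAEs in all groups. The request to come forward is shorter than the collection period, and no planned contact fills the difference. The gap is 188 days (62.7% of follow-up) if the window follows each dose, or 145 to 237 days with visit windows timed from the previous visit. If the window follows the first dose only, 210 days depend on the final visit. The choice between these readings is an assumption, because 9.3 does not settle it. The likely effect is late, and possibly incomplete, knowledge of SAEs. It is not a total absence of ascertainment.

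For children the point concerns SAEs only. It is tempting to conclude that adult event rates before and after about D112 would not be comparable. That does not follow, because whether adult non-serious events are recorded beyond 30 days depends on two sentences in 11.3.6 that disagree.

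This is an inexpensive improvement worth making, and it does not undermine the trial's design.

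**What to change.** 1. In 9.3 and the volunteer instructions, ask all volunteers and carers to notify the study team of any hospital admission, death or serious illness at any time up to the D300 visit. The 56-day request for other illness can stay.
2. State in 9.3 whether the 56 days run from each vaccination or from the first only.
3. In 11.3.6, reconcile the 30-day recording limit that names no group with the provision for Group 1 throughout the study. Then match the adult request for non-serious illness to whichever period is confirmed.

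The cost is one added sentence, two clarifications and a matching line in the volunteer instructions. No scheduled visit is added. The downside is a few more unscheduled contacts. With item 1 in place, the interval with no SAE reporting request falls to 0 days.
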